Appendix C (The IRB-approved Protocol)

Table 7. Timeline for collection of field samples.

Information/Sample	Day 1	Day 2	Day 3	Day 4	Day 5
Indoor air – active	Setup				Collect
Indoor air – passive	Setup				Collect
Electrostatic dust collector (main play area, duplicate)	Setup				Collect
Surface dust by Swiffer					Collect
Questionnaire					Collect
Consumer product inventory	Collect				
Housing and community information ^a	Collect				
Surface wipes (kitchen & bathroom, n=8)	Collect				
Socks	Instructions ^b	Collect			Retrieve
Duplicate diet (n=9) ^{a,e}	Instructions ^b	Collect			Retrieve
GPS and accelerometer	Instructions ^b	Collect	Collect	Collect	Retrieve
Urine (toilet trained sibling) ^c	Instructions ^b		Collect	Collect	Retrieve
Urine-diaper (non-toilet trained sibling) ^c	Instructions ^b		Collect	Collect	Retrieve
Feces ^{a,e}	Instructions ^b		Collect		Retrieve
Toenail ^{a,e}	Collect				
Blood ^{a,d,e}	Collect				
Soil	Collect				
Household vacuum bag					Collect (if available)
Technician vacuum sample					Collect
Hand wipe					Collect

^aThese sample types will only be collected at the baseline visit.

^bInstructions will be given to the caregiver for the use/collection of socks, duplicate diet, GPS, accelerometer, urine (cup or diaper), and feces on Day 1. During Days 1-5, the caregiver will complete the associated tasks to allow for retrieval of these data, items, and samples on Day 5.

^cOnly one type of urine sample will be collected for the sibling, depending on whether they are toilet trained. Diapers collected must contain only urine. First morning voids will be collected for toilet trained children on 2 days; first morning voids or convenience samples will be collected for non-toilet trained children on 2 days.

^dSibling blood samples are optional.

^eDuplicate diet, feces, toenail clippings, and blood samples must be collected from the same participant (either the index child or sibling).

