4.4.3 Biological Samples

[figure not shown]
Urine and blood samples are being collected from the index children as part of the Green Housing Study protocol. An aliquot of these samples will be used to analyze for select biomarkers. Additional biological samples to be collected from the index child are toenail clippings. Urine, blood, toenail clipping, and fecal samples will be collected from the sibling(s) of the index child (Table 4). Urine samples will be collected as first morning voids. Diapers containing only urine will be collected for non-toilet trained siblings, with a preference for first morning voids, followed by a convenience sample. Collection of blood from siblings is an optional item for participants. Toenail clippings and feces will be collected by the mother/caregiver and analyzed for the metals listed in Table 6. In the event that a blood sample is not collected from the sibling, then every effort will be made to collect the toenail clipping and fecal samples from the index child in order to have a matched sample set for metal analysis (i.e., duplicate diet, blood, toenail clippings, feces).

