4.4.4 Accelerometer and GPS

Activity and location data will be collected from both the index child and sibling on Days 2-4 of the study using minimally burdensome technologies, namely a waistband-mounted accelerometer-based activity monitor (Actical™; Philips Respironics, Bend, Oregon) and a Global Positioning System (GPS) Data Logger (model BT-Q1000XT; Qstarz International, Taipei, Taiwan). Field study technicians will prepare the devices for data collection and instruct participants on placement and use of the devices. Both devices will be worn by study participants during awake periods for all three days; the final day of data collection will correspond to the day covered by the EPA pilot study add-on questionnaire (collected on Day 5; questions are answered by participants for activities and locations for the preceding day, i.e., Day 4). The Actical™ requires no recharging during the data collection period; the BT-Q1000XT Data Logger will require recharging by the study participant's caregiver each evening. The devices will be collected by the field technician on Day 5 and the collected data downloaded and stored. Figure 1 shows the data flow for the accelerometer and GPS data.

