Appendix C (The IRB-approved Protocol)

Objective 1: Identify and characterize factors affecting children's exposures to chemical ingredients from consumer products found in their everyday environment in order to support the data and modeling needs of the exposure components of EPA's national research programs

The data analysis goal for objective 1 is to identify predictive factors associated with children's exposures to chemical and biological contaminants in their residential environments, with a focus on consumer product chemicals. Exposure factors of interest include housing characteristics, human activity, consumer product presence/use, and environmental contaminant concentrations and distributions. Exposure factor assessment will inform development and evaluation of exposure models for children. Identification of predictive factors that differ between green and traditional housing may also enhance CDC's ability to examine asthma outcomes in the Green Housing Study. Data analyses for this objective will be integrated with those for other objectives (particularly objectives 2, 4, 5, and 8).

Descriptive and summary univariate statistics will be compiled for measurement and survey data to identify variables with sufficient measurable results and variability to consider in factor analysis. Spearman/Pearson correlation analyses will be performed within and between all measurement data to elucidate relationships and associations. Geometric mean and geometric standard deviations will be calculated for target analytes by sibling/age groups. T-tests and/or F-tests of differences between measurement distributions across sibling/age group and other categorical product, housing, and activity factors will be calculated. In some cases, factor assessment by survey and activity data categories may require non-parametric tests. Where there are sufficient data, regression model analysis with target analyte measurements as outcome variables and product, activity, location, and housing variables as potential exposure factors will be constructed to examine relative contributions to variability in children's exposures. A specific goal of the analysis is to determine how, and to what extent, child activity factors might influence relationships between environmental contaminant levels and exposures as measured from hand wipe, sock, and biomarker concentrations.

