Appendix C (The IRB-approved Protocol)

14. How many times did your child wash his/her hands yesterday?

- 1
- 2
- 3
- 4
- 5
- 6
- 7
- More than 7
- Don't know/Refused to answer

15. How many times a week does your child bathe?

- 1
- 2
- 3
- 4
- 5
- 6
- 7
- More than 7
- Don't know/Refused to answer

D. Diet Questions (To be completed by field technician and participant)

16. How many meals did your child eat yesterday (e.g., breakfast, lunch, dinner), not counting snacks?

- 1
- 2
- 3
- 4
- 5
- 6
- 7
- More than 7
- Don't know/Refused to answer

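### The socks and the siblings' first morning voids are taken before all or nearly all of the behaviour recorded in the Day 4 diary, which weakens Objective 1's analysis of activity against these exposures

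*Protocol*

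**What the plan says.** **Sampling days.** Table 7 (Section 4.4) has socks collected on Day 2, sibling urine on Days 3 and 4, and the questionnaire and hand wipe on Day 5. The same five-day pattern applies in each of the four visit periods. Footnote c to Table 7 says "First morning voids will be collected for toilet trained children on 2 days" and continues: "first morning voids or convenience samples will be collected for non-toilet trained children on 2 days". Section 4.4.3 gives the order of preference for diapers: "Diapers containing only urine will be collected for non-toilet trained siblings, with a preference for first morning voids, followed by a convenience sample". Index-child urine is an aliquot from the parent study (Table 4), and Table 7 assigns it no day.

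**Recall day.** Section 4.4.4 says of the questionnaire collected on Day 5 that "questions are answered by participants for activities and locations for the preceding day, i.e., Day 4". In the Appendix C questionnaire, items 3 and 5 are half-hour grids for location and activity. Item 14 asks "How many times did your child wash his/her hands yesterday", and items 16 and 17 ask about yesterday's meals.

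**Devices.** Accelerometer and GPS are worn by both children on Days 2 to 4 (Section 4.4.4).

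**Intended use.** Objective 1 is a primary objective. Section 5.0 sets it the specific goal of learning how, and how far, "child activity factors might influence relationships between environmental contaminant levels and exposures as measured from hand wipe, sock, and biomarker concentrations".

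**The concern.** An exposure sample can reflect only what happened before it was taken. If the recorded behaviour comes later, any association depends on how closely the recalled day resembles the days before it, whatever the half-life of the analyte. That tends to pull associations towards zero.

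This matters because Section 2.2 hypothesises that personal factors, activities and behaviours among them, are the main influence on exposure. A weak or null diary association with sock loadings or urinary biomarkers could be read as evidence against that hypothesis when the timing alone might explain it. The protocol does not mention the mismatch. The authors did attend to alignment elsewhere: Section 4.4.4 makes the last device day the same as the questionnaire's recall day.

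**Working it through.** The plan states no figure on this point, so the check sets the days side by side.

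| Objective 1 measure | Day (Table 7) | Against the Day 4 diary | Against device data, Days 2-4 |
|---|---|---|---|
| Socks | 2 | 2 days before | on the first device day |
| Sibling void 1, first morning | 3 | 1 day before | after 1 device day |
| Sibling void 2, first morning | 4 | same date, before most of the day | after 2 device days |
| Sibling void 2, convenience diaper | 4 | may be during or after Day 4 activity | after 2 device days or more |
| Hand wipe | 5 | 1 day after | after all 3 device days |

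**How much of Day 4 follows a Day 4 first morning void?** The grids run from 5:00 am to 11:59 pm, which is 19 hours × 2 = 38 half-hour slots. The protocol gives no void time, so 6:00 to 8:00 am is assumed.

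- Void at 6:00 am: 2 slots precede it and 38 − 2 = 36 follow (36/38 = 95%).
- Void at 8:00 am: 6 slots precede it and 38 − 6 = 32 follow (32/38 = 84%).

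**Which questionnaire content is tied to Day 4?**

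- Tied to Day 4: the location and activity grids (items 3 and 5), hand washing (item 14) and yesterday's meals (items 16 and 17). The activity grid holds the child's timed record of grooming or bathing, chores and pet contact.
- Not tied to Day 4: floor time and surface (items 8 and 9), usual outdoor and park play (items 10 to 12), weekly bathing (item 15), food, store and restaurant frequency (items 18 to 20) and product-use frequency (items 21 to 23).

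**What would attenuation look like?** The documents give no day-to-day correlation of activity. Suppose one diary-day predictor, an exposure caused by a single earlier day, equal variance on both days and correlation r between them. The slope is then multiplied by r and the explained variance by r². For an assumed r of 0.3 to 0.7, slopes fall to 30-70% and explained variance to 0.3² = 9% through 0.7² = 49% of the same-day values. This illustrates the mechanism and does not estimate the loss in this study.

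**The case against.** The strongest reply is that Objective 1 does not rest on the diary. Table 8 lists questionnaire and activity data together. The devices overlap the sock day and precede both first morning voids, and the habitual items do not depend on Day 4 at all. Section 5.0 does not say that diary variables will be regressed on sock or void results, makes the regressions conditional on sufficient data, and may leave the choice of pairing to a statistical analysis plan.

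Much of this stands, and it rules out several stronger readings that a reader might infer:

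- *Both voids come before the recall day.* The second is collected on Day 4 itself; only the order within that day is the problem.
- *Nothing done on Day 4 can affect either void.* A convenience diaper may be collected later that day. Section 3.3.1 names ages 0 to 3 as the group of most interest, so this may not be rare, although first morning voids are preferred.
- *All activity information comes from Day 4.* Bathing, diet, product use, floor time and outdoor play also have habitual items.
- *The hand wipe is mistimed too.* It follows the recall day and is correctly ordered.
- *Biomarkers are mistimed for both children.* The index child's urine day is not given, so the point covers sibling urine only.

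Two things remain. Devices record movement and place, not grooming, chores or pet contact, and Section 4.5 says the activity questions focus on activities of that kind. The typical-day question (item 4) asks about locations, not activities. Also, an analysis plan can choose the pairing, but it cannot change the day on which a sample was taken.

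**Conclusion.** The concern holds in a limited form. For the socks and the siblings' first morning voids, the day-specific diary items describe later behaviour: wholly later for the socks and the Day 3 void, and for 84-95% of the slots for a Day 4 void, given the assumed 6:00 to 8:00 am collection. For these measures the diary can serve only as a proxy for earlier days, and that part of Objective 1 is weakened in all four visit periods. Device data and habitual items offset the loss in part.

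The size of any attenuation is not known from the documents. A reader might take the 30-70% slope range as the expected loss, but it rests on an assumed correlation and a single-day exposure model, and it does not apply to device or habitual variables. The mismatch is worth correcting because it touches a primary objective, cannot be repaired after collection and is cheap to remove.

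**What to change.** In Table 7:

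- Keep the Day 3 sibling void, which follows the Day 2 duplicate diet.
- Move the second sibling void from Day 4 to the first morning void of Day 5, for pick-up at that day's visit.
- Move sock wear from Day 2 to Day 4.

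In Objective 1, pair the Day 4 diary items (the grids, hand washing and meals) with the Day 5 void, the Day 4 socks and the Day 5 hand wipe. Use device data and habitual items for the Day 3 void. The pairing rule should cover the day-specific items only, so that habitual items remain usable with every sample.

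The cost is an edit to Table 7 and the caregiver instructions. The number of samples and visits is unchanged, and footnote b already has caregivers completing tasks over Days 1 to 5 for retrieval on Day 5. Moving the socks gives up their present place before the Day 3 void, but on Day 4 they would precede the Day 5 void and match both the diary and the devices. The small downside is that the Day 5 void must be ready at pick-up.

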Appendix C (The IRB-approved Protocol)

4.4.1 Environmental Samples

Additional environmental samples will be collected for analysis of chemicals of interest to EPA. Collection of field samples will be carried out by trained technicians using standardized protocols. A quality assurance project plan (QAPP) and standard operating procedures will be prepared and approved prior to collection of field samples. Field staff will be trained by CDC and EPA personnel. Environmental samples will include indoor air, house dust, soil, and surface wipes.

An indoor air sample will be collected from the main play area in the home. Both passive and active air sample collection will be used. The active air sampling approach will use low volume air samplers placed in a childproof, sound-proof housing and located in the child's play area. The pump flow rate will be sufficiently low to ensure that the pump can run for 5 consecutive days with minimum disruption to the study participants. A polyurethane foam (PUF) filled glass tube will be combined with a quartz or Teflon particle filter for collecting semi-volatile target analytes. Passive air collection will be performed by deploying a sorbent tube diffusion sampler in the child's play area. The passive sampler will collect volatile target analytes. The tube cap will be removed on the first day of sampling, and will be replaced on the return visit on Day 5.

House dust samples will be collected from a floor (preference: carpeted surface; alternate: hard surface) where the children may play or spend time. House dust will be collected using a forensic vacuum equipped with an in-line filter to collect and trap surface dislodgeable particles. The sampled area will be measured, marked, and recorded to ensure accurate documentation of amount of available dust for chemical and biological analyses. If available, field technicians will collect a participant's household vacuum cleaner bag. A swiffer settled dust collection protocol will also be used to collect settled dust from the tops of door jambs and bookcases. Dust samples will also be collected from the aforementioned areas using an electrostatic dust collector (EDC). Two EDCs will be placed horizontally at surfaces at least 1.5 meters above the floor and exposed for five days.

Surface wipe samples will be collected from impervious surfaces (e.g., hard floors, countertops) in a location where the children may spend time and/or locations where consumer products are stored and used (e.g., kitchen, bathroom). Multiple surface samples will be collected by wiping within a 144 square inch template placed on the impervious surface. Surface wipe samples will be gathered on cotton wipe media wetted with 6-mL of isopropanol.

Soil samples will be collected from an outdoor location in closest proximity to where the children spend time playing when outdoors. Soil samples will consist of scrapings collected to a depth of 2-3 inches using a pre-cleaned scoopula and placed into 8 oz. amber glass jars.

Appendix C (The IRB-approved Protocol)

4.4.2 Personal Samples

Personal samples will include hand wipes, socks (to obtain surface-to-sock loadings), and a 24-hour duplicate diet. Hand wipes will be collected from the right and left hands of the sibling and index child. Cotton wipe media wetted with isopropanol will be used to wipe both hands.

The duplicate diet will be collected from only nine participants to minimize study burden. Preference will be given to homes where blood, toenail, and fecal samples are collected for the siblings. Duplicate diet will include both food and drink for a 24-hour period and analyzed for the metals listed in Table 6. Each participant will be provided with clean containers for the food and drink collection. Samples will be kept cool until picked up by the field technician.

4.4.3 Biological Samples

[figure not shown]
Urine and blood samples are being collected from the index children as part of the Green Housing Study protocol. An aliquot of these samples will be used to analyze for select biomarkers. Additional biological samples to be collected from the index child are toenail clippings. Urine, blood, toenail clipping, and fecal samples will be collected from the sibling(s) of the index child (Table 4). Urine samples will be collected as first morning voids. Diapers containing only urine will be collected for non-toilet trained siblings, with a preference for first morning voids, followed by a convenience sample. Collection of blood from siblings is an optional item for participants. Toenail clippings and feces will be collected by the mother/caregiver and analyzed for the metals listed in Table 6. In the event that a blood sample is not collected from the sibling, then every effort will be made to collect the toenail clipping and fecal samples from the index child in order to have a matched sample set for metal analysis (i.e., duplicate diet, blood, toenail clippings, feces).

4.4.4 Accelerometer and GPS

Activity and location data will be collected from both the index child and sibling on Days 2-4 of the study using minimally burdensome technologies, namely a waistband-mounted accelerometer-based activity monitor (Actical™; Philips Respironics, Bend, Oregon) and a Global Positioning System (GPS) Data Logger (model BT-Q1000XT; Qstarz International, Taipei, Taiwan). Field study technicians will prepare the devices for data collection and instruct participants on placement and use of the devices. Both devices will be worn by study participants during awake periods for all three days; the final day of data collection will correspond to the day covered by the EPA pilot study add-on questionnaire (collected on Day 5; questions are answered by participants for activities and locations for the preceding day, i.e., Day 4). The Actical™ requires no recharging during the data collection period; the BT-Q1000XT Data Logger will require recharging by the study participant's caregiver each evening. The devices will be collected by the field technician on Day 5 and the collected data downloaded and stored. Figure 1 shows the data flow for the accelerometer and GPS data.

Appendix C (The IRB-approved Protocol)

Figure 1.

4.4.5 Sample Processing and Shipment

Throughout the duration of the EPA pilot study add-on, chain of custody will be maintained for all samples collected in the field. Sample media will receive unique, individual labels and will be logged in the field to establish sample identification and chain of custody. All samples will be stored in a cooler at reduced temperatures during field collection and subsequently stored at -4°C prior to shipping to the U.S. EPA laboratory in Research Triangle Park, NC. Upon receipt at the laboratory, the samples will be logged and stored at -20°C or less.

4.4.6 Sample Analysis

[figure not shown]
Organic chemical target analytes and biomarkers will be extracted from samples by one of several techniques such as pressurized fluid extraction, sonication, or Soxhlet. These compounds will be separated by gas or liquid chromatography and quantified using mass spectrometry. Metal target analytes will be extracted from samples by microwave digestion and analyzed using inductively coupled plasma mass spectrometry. Mold target analytes will be extracted using a liquid shaker technique and analyzed using mold specific quantitative polymerase chain reaction and high-throughput DNA sequencing.

Appendix C (The IRB-approved Protocol)

4.5 Questionnaire

One questionnaire will query participants on location, transportation, activity, diet, and consumer products use and will be used by the field staff to record home observations (Appendix C). It will complement the questionnaires currently being used in the Green Housing Study and will be administered using a conventional pen and paper approach to the mother/caregiver for the index child and participating sibling(s). The questionnaire is primarily a recall questionnaire covering the activities of the index child and sibling(s) on the day prior to each field visit. Figure 2 shows the data flow for the questionnaire.

Figure 2.

Questions will gather information on the types of locations the children visited throughout the day, including residences, non-residential indoor environments (e.g., schools and stores), and outdoor environments. In order to reduce burden, questions will be asked about the 5 locations where each child spent the most total time. A series of transportation questions will also be asked related to how the children moved from one location to another to characterize time spent in vehicles or other near-road locations (e.g., street or bus stop). Questions will also ask about the types of activities performed in each location, with a primary focus on activities relevant to exposure to consumer products (e.g., bathing or grooming activities, chores, and contact with pets); however, other general categories of activities are included for estimating an overall level of energy expenditure for each child relevant to intake dose rates of indoor chemicals.

